We believe that the process of undergoing a fertility preservation consultation and/or undergoing an oocyte harvest in itself has a potential therapeutic benefit. Focusing on, “after” a patient’s cancer diagnosis has been suggested to have a positive effect on a

patient's psychosocial state. We wish to explore this theory with implementation of a follow-up interview and the validated Ferti-Qol questionnaire to assess a patient's quality of life. (Boivin et al, 2011) We also plan to assess egg quality in all of our patients to determine the impact of patient demographics and various chemotherapeutics.

Purpose & Objective

Purpose: This investigational study will permit patients to cryopreserve their oocytes, after first obtaining full written informed consent, for the purpose of potential future use under the oversight of the institutional review board, as specified by ASRM and ACOG current guidelines. The data obtained will also contribute to the knowledge base surrounding quality of life issues and fertility preservation in general, and oocyte cryopreservation in particular.

Objective: To determine the long term benefits, in particular impact on patient quality of life and clinical outcomes associated with the use of oocyte cryopreservation as an investigational option for women who wish to preserve their fertility, to assess egg quality and determine how patient demographics and various chemotherapeutics may affect it.

Hypothesis: Oocyte cryopreservation, which is currently investigational and requires IRB oversight, may be an effective and safe method of fertility preservation for women who may be facing the loss of future fertility due to medical or non medical reasons, with resulting future successful pregnancies. The process of fertility preservation will have a perceived improvement on patient quality of life. Egg quality will be impacted by patient age and alkylating chemotherapy but not other agents or demographic characteristics.

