The ASRM and ACOG practice guidelines stating that oocyte cryopreservation is still considered investigational and may only be offered with appropriate informed consent in a research setting with IRB oversight necessitate more rigorous investigation into the methods and consequences of oocyte cryopreservation in order for it to evolve from an experimental to a standard procedure,. To this end, this protocol has been designed to identify suitable candidates for oocyte cryopreservation and to systematically follow them in order to assess the long term benefits and outcomes associated with its use. During our investigation we will explore egg quality and quality of life measures.

Lastly, the implementation of fertility preservation counseling and obtaining of oocytes for future use is believed to have a positive impact on a cancer patient's quality of life. We will obtain a structured fertility focused quality of life questionnaire and survey to assess one year after harvest the impact of the process. We will compare cancer patients to those patients undergoing oocyte cryopreservation for non-medical reasons.

Study Design

Research Design & Methodology: We will conduct a prospective study to assess the long term benefits and outcomes of the existing oocyte cryopreservation methods for fertility preservation in women with a potential medical or non medical risk of loss of fertility. Women wishing to preserve their oocytes using cryopreservation will be informed of the risk and limitations of the procedures involved in ovarian hyperstimulation, oocyte recovery, cryopreservation and subsequent viability after warming. Women who consent to the procedure will undergo standard controlled ovarian hyperstimulation (COH) and oocyte retrieval procedures currently in use for IVF. Following harvest all eggs obtained will be evaluated for degree of fragmentation and maturation status. The oocytes will be cryopreserved using kits of media and devices currently approved for use in the vitrification of fertilized eggs and embryos, and the cryopreserved oocytes will be stored for future patient use in a long term storage facility in Minnesota (Reprotech Ltd.). Patients with stored oocytes will be contacted annually to determine the outcome of any oocyte warming procedures (oocyte thawing, fertilization and embryo transfer).

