We will obtain a structured fertility focused quality of life questionnaire (FertiQol) and survey to assess one year after harvest the impact of the process. We will compare cancer patients to those patients undergoing oocyte cryopreservation for non-medical reasons. FertiQol is scored based on the standards of the assessment tool in a quantitative manner. The structured interview will be assessed in a qualitative manner.

Duration: Until the completion of our investigational study and the patient outcome follow-up one year following oocyte harvest.

Location: Female patients will be identified and consented and all study procedures will be conducted through the Division of Reproductive Endocrinology and Infertility, Department of Obstetrics and Gynecology, University of Illinois at Chicago (UIC).

Participant Selection and Enrollment

This study will enroll up to 50 women of reproductive age over 5 years at UIC, in three different categories:

1. Women of reproductive age who are diagnosed with cancer or any disease whose treatment or its progression may impair their reproductive potential.
2. Women undergoing standard In Vitro Fertilization to treat infertility who experience unforeseen events that halt the treatment cycle, such as adverse reactions to hormonal hyperstimulation, inappropriate endometrial receptivity, inability of the partner to provide a semen sample on the day of the egg retrieval or who are unable to consent to freezing of embryos so that the eggs can be cryopreserved and not discarded, as is standard procedure currently.(e.g., failed testicular sperm aspirations, inability to collect or unexpected need to be out of town or patients with ethical objections to freezing of embryos).

3. Women seeking oocyte cryopreservation for non medical reasons such as deferred childbearing.

Women seeking fertility preservation are referred for a comprehensive consultation with a Reproductive Endocrinologist to discuss the range of treatment options available to her. Only patients who choose oocyte cryopreservation as their method of fertility preservation will be enrolled in the study.

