Specifically, they will agree to notify the investigators of any changes in their contact information. Study participants will be contacted on an annual basis using the "Investigational Oocyte Cryopreservation Follow-up Call Script" to determine any subsequent attempts to utilize the stored oocytes for the purpose of initiating a pregnancy, along with the outcome of the attempt. An additional follow up email script will also be added to this research. In addition, patients will complete the Ferti-Qol questionnaire at the one year time point. All other dispositions of the oocytes will also be recorded. Individual files will be kept active until all oocytes have been utilized, disposed of in some other way, or ten years following storage, whichever comes first. Patients will be assigned a research number and data will be de-identified. All de-identified data and the master code list will be stored in a locked file cabinet in a locked office and in a password-protected computer in a locked office by the PI and only the co-investigators and the PI will have access to the data.

The subject's participation in this study may involve the following risks;

Standard Ovarian Stimulation: The ovarian stimulation step often causes a sense of fullness or bloating, which usually goes away within a few days after the retrieval. In about 1% cases, patients will develop ovarian hyperstimulation syndrome (OHSS) a serious complication resulting in the accumulation of fluid in the abdominal cavity. This

complication is self-limited, but severe cases may require several days of hospitalization for fluid management. In patients facing a cancer diagnosis, the use of fertility medication will cause a significant increase in two ovarian hormones, estrogen and progesterone, which could potentially worsen the prognosis for the cancer. However, in the case of most cancers the use of fertility drugs does not appear to worsen the chances for cure. Nevertheless, patients will need to discuss with their medical oncologist the pro's and con's of fertility drug use prior to undertaking oocyte cryopreservation.

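### FertiQoL is collected only once, a year after harvest, and only in women who had the procedure, so it cannot show the hypothesised improvement in quality of life

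*Protocol*

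**What the plan says.** The hypothesis under Purpose & Objective is directional: "The process of fertility preservation will have a perceived improvement on patient quality of life". The objective in the same section singles out the effect on quality of life. The background text just before it says what the process is: "We believe that the process of undergoing a fertility preservation consultation and/or undergoing an oocyte harvest in itself has a potential therapeutic benefit". It also says how the idea will be examined: "We wish to explore this theory with implementation of a follow-up interview and the validated Ferti-Qol questionnaire". The Rationale makes the theory specific to cancer: counselling and obtaining oocytes "is believed to have a positive impact on a cancer" patient's quality of life.

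On timing, the document is consistent. Study Design plans a "structured fertility focused quality of life questionnaire (FertiQol) and survey to assess one year after harvest the impact of the process", and the Rationale says the same. Under Study Procedures, Quality of Life Assessment: "In addition, patients will complete the Ferti-Qol questionnaire at the one year time point". No earlier administration appears anywhere. The counselling and psychological assessment before entry concern consent and coping, and are not described as a quality-of-life measurement.

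On comparison, the Rationale and Study Design both say: "We will compare cancer patients to those patients undergoing oocyte cryopreservation for non-medical reasons". Participant Selection and Enrollment restricts entry to women who have opted for oocyte cryopreservation. Study Design states that FertiQoL is scored quantitatively and the interview qualitatively. It gives no scoring for the survey.

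**The concern.** Improvement is a change, so it needs an earlier score. An effect of the process also needs some comparison with women who did not go through it. FertiQoL as scheduled has neither. Followed exactly, the plan yields a one-year score for each group and a difference between groups, and neither says whether scores rose or fell in anyone.

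The planned contrast does not fill the gap, because both groups undergo the process and any effect common to them cancels. If the effect is larger in cancer patients, as the Rationale may imply, the contrast does move. It then shows only the difference between two effects, confounded with how the groups started and with cancer and its treatment.

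This touches a stated objective, and the Conclusion lists the quality-of-life assessment among the data meant to support offering the procedure with confidence. It is also a matter of data collection, so an analysis plan written later cannot repair it.

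**Working it through.** The protocol gives no SD, effect size, power, completion rate or split of its maximum of 50 women across three categories, so there is no figure of its own to reproduce. The check is whether the planned data determine the target, and then how precise the estimates could be under stated assumptions.

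**1. What the contrast estimates.** For cancer (C) and non-medical (N) patients, the expected one-year difference is

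D = (baseline_C − baseline_N) + (process_C − process_N) + (course_C − course_N),

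where course is change over the year that is not due to the process. Mean change in a group is process + course. With assumed values in SD units and course_N = 0:

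| Baseline gap C−N | process_C | process_N | course_C | D | Change C | Change N |
|---|---|---|---|---|---|---|
| 0 | −0.5 | −0.5 | 0 | 0 | −0.5 | −0.5 |
| 0 | 0 | 0 | 0 | 0 | 0 | 0 |
| 0 | +0.5 | +0.5 | 0 | 0 | +0.5 | +0.5 |
| 0 | +0.5 | 0 | 0 | +0.5 | +0.5 | 0 |
| 0 | +1.0 | +0.5 | 0 | +0.5 | +1.0 | +0.5 |
| 0 | 0 | −0.5 | 0 | +0.5 | 0 | −0.5 |
| +0.5 | 0 | 0 | 0 | +0.5 | 0 | 0 |
| −0.5 | +0.5 | 0 | 0 | 0 | +0.5 | 0 |
| 0 | +0.5 | 0 | −0.5 | 0 | 0 | 0 |
| 0 | 0 | 0 | +0.5 | +0.5 | +0.5 | 0 |

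D alone cannot tell harm, no effect and benefit apart (rows 1 to 3). Nor can it tell benefit in C from harm in N or a baseline gap (rows 4 to 7). The change columns, which need a baseline, do show whether scores rose or fell. In the last two rows course acts, and change does not isolate the process effect even with a baseline.

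**2. The same point in raw scores.** Assume one-year means of 60 (cancer) and 70 (non-medical). If cancer patients had started at 50, 60 or 70, their change would be +10, 0 or −10. The observed difference is −10 in all three cases.

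**3. Precision.** 95% CI half-widths in SD units, with n completers per group and correlation r between baseline and one-year score (all assumed):

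- Contrast without baseline: t(0.975, 2n−2) × √(2/n)
- Contrast adjusted for baseline, approximate: t(0.975, 2n−3) × √(2/n) × √(1−r²)
- Mean change within a group: t(0.975, n−1)/√n × √(2(1−r))

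At n = 13 and r = 0.5: 2.064 × 0.392 = 0.81; 2.069 × 0.392 × 0.866 = 0.70; 2.179/3.606 × 1 = 0.60.

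| n per group | Contrast, no baseline | Adjusted, r = 0.5 (r = 0.3 to 0.7) | Mean change, r = 0.5 (r = 0.3 to 0.7) |
|---|---|---|---|
| 8 | 1.07 | 0.94 (1.03 to 0.77) | 0.84 (0.99 to 0.65) |
| 13 | 0.81 | 0.70 (0.77 to 0.58) | 0.60 (0.72 to 0.47) |
| 17 | 0.70 | 0.61 (0.67 to 0.50) | 0.51 (0.61 to 0.40) |
| 25 | 0.57 | 0.49 | 0.41 |

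The last row would require all 50 women to fall in these two groups and all to complete. Without a baseline, the mean-change column does not exist at any sample size.

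**The case against.** The strongest reply is that the hypothesis concerns perceived improvement, which can be asked about in retrospect. The protocol pairs FertiQoL with an interview and a survey, and these may well capture it. That stands, and no claim is made here about either tool. But the protocol also enlists FertiQoL for this theory, and says that questionnaire and survey together are "survey to assess one year after harvest the impact of the process". FertiQoL is the only quality-of-life tool stated to be scored quantitatively.

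A second reply is that a baseline would not deliver what is missing. There would still be no unexposed group, and disease course could imitate or mask an effect (the last two rows of the first table). For cancer patients this is the expected case, because a baseline would fall in the short deferral period before therapy. A baseline after consent would also miss any effect of the consultation, which the protocol counts as part of the process. All of this is true. A baseline measures change without attributing it. Measured change is still more than the present schedule provides, and it removes the starting-level gap as an explanation.

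A third reply is that one-year scores can still be described and compared between groups, and that calling them descriptive would avoid misinterpretation. That is right, and it is the fallback below. It keeps the claim honest but leaves the objective unanswered by this instrument.

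**Conclusion.** The point holds. As scheduled, FertiQoL cannot quantify improvement in any woman or group, and the cancer versus non-medical contrast is compatible with benefit, no effect or harm. This follows from the timing and the enrolment rule and does not depend on any assumed number. The half-widths do rest on assumed group sizes and correlations. They show that precision is low with or without a baseline: 0.81 against about 0.70 SD for the contrast at 13 per group, and 0.57 against 0.49 SD even at 25 per group. The main gain from a baseline is therefore that change becomes estimable; the gain in precision is secondary. This should be fixed, and soon, because the information is lost for each woman enrolled without a first score.

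**What to change.** 1. In the Quality of Life Assessment section, add FertiQoL at enrolment, after informed consent and before stimulation starts, and keep the one-year administration.
2. Report within-woman change with a 95% CI by enrolment category for every woman with a pre-stimulation score. Include any such women in the IVF category, for example those known beforehand to object to freezing embryos. In the medical category, show cancer separately from other disease.
3. For women without a pre-stimulation score, such as those enrolled because of an event on the day of retrieval, report one-year scores descriptively.
4. Keep the cancer versus non-medical contrast, adjusted for baseline score.
5. State the limits. Change is uncontrolled and reflects time, disease course and treatment. In cancer patients it may be recovery from the period just before therapy. The baseline misses the earlier consultation and possibly the required mental-health counselling, which Study Procedures lists before consent. Precision will be low.

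If no baseline is added, describe the FertiQoL result as a one-year comparison and do not use it as evidence of improvement.

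The cost is one short questionnaire per woman, a protocol amendment and a small patient burden. Women already enrolled, and those entering after stimulation has begun, will have no baseline, so the change analysis will cover fewer than the 50 women.

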Chen reported the first successful attempt at cryopreserving and thawing a human oocyte – a twin pregnancy resulted after *in vitro* fertilization and embryo transfer (Chen, 1986). Progress in the field moved slowly for the next decade after murine data suggested that cryopreserved oocytes showed higher levels of chromosomal anomalies when compared with fresh oocytes (Johnson & Pickering, 1987). However, work in the early 1990s by Gook et al. demonstrated that cryopreservation was not as detrimental as originally thought, leading to renewed research interest in human oocyte cryopreservation (Gook et al., 1994). By 2004, 100 human babies had been born from cryopreserved oocytes. However, these infants were produced with great inefficiency (Stachecki & Cohen, 2004). For instance, Marina & Marina (2003) reported a 4% live birth rate from 99 frozen oocytes and results with larger sample sizes were even less impressive; 16 pregnancies from 1502 thawed oocytes (Porcu et al., 1999). Breakthroughs made by Italian researchers in optimizing freezing and thawing methods greatly improved pregnancy rates with mature human oocytes yielding pregnancy rates per thaw cycle of 10% which compares favorably with the natural fecundity rate of 20% per cycle (Coticchio et al., 2006; Paynter et al., 2005; Fabbri et al., 2001; Bianchi et al., 2007; Borini et al., 2004; Borini et al., 2006; Grifo and Noyes, 2009; Nagy et al., 2009). However, these results are still well below the pregnancy rates for fresh IVF cycles in women under the age of 37 years (45-55% live-birth rate).

There is little doubt that oocyte cryopreservation offers a reasonable fertility preservation option for cancer patients. However, it is imperative that follow-up data regarding the actual efficacy of this approach and the health of infants born following its use be prospectively generated, notwithstanding the difficulties inherent in the time frame over which patients might need to be followed.

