Data Safety & Monitoring: The principal investigator and co-investigators will monitor the subject records every 6 months for completeness and to determine whether any new information has become available, which may impact continuation of this study. Any adverse events or complaints will be reported to the IRB with the appropriate notification form.

Criteria for Terminating the Study: Once the risk/benefit ratio of the protocol becomes unfavorable, where the subject is exposed to greater harm than potential benefit, the study will be terminated. Notice of study termination will be submitted to the University of Illinois at Chicago's IRB.

Procedures for Reporting Deviations from the Original Plan: Any deviations from the original protocol that take place during the course of the study will be reported in a timely fashion to University of Illinois at Chicago's IRB in the form of a revision or safety/other submission.

Conclusion

Fertility preservation ranks as one of the greatest concerns for women diagnosed with cancer as well as those fearing loss of fertility due to deferred childbearing. Therefore, establishing the effectiveness and safety of oocyte cryopreservation as a fertility preservation option would greatly impact the reproductive destinies of women undergoing fertility-threatening treatment. The psychosocial impacts of fertility preservation and oocyte harvest are not well established. At the conclusion of the study, we hope to have sufficient data to assess the long term benefits and outcomes of oocyte cryopreservation, including information regarding the future use of cryopreserved oocytes, their survival and viability, pregnancy and live birth outcomes, as well as quality of life assessment, so as to confidently offer the procedure as a safe and effective method of fertility preservation. We also hope to build on the current understanding of the factors that impact egg quality; another key aspect of success and thus patient consultation.

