Anticipated Results & Potential Pitfalls: It is anticipated that oocyte cryopreservation will provide a scientifically sound fertility preservation option for cancer patients and for women who wish to delay child bearing. While the cryopreservation procedure is still experimental, early findings have demonstrated promising results. The findings from this study will contribute to the existing knowledge base by providing valuable evidence about how to perfect the cryopreservation process and increase pregnancy rates in women whose oocytes have been frozen and thawed and to document the long term outcomes from the use of these oocytes (pregnancy rates and rate of birth defects).

References

American College of Obstetrics and Gynecologists. (2008) ACOG Committee Opinion. Ovarian tissue and oocyte cryopreservation. *Obstet Gynecol*; 111(405):1255-56.

American Society for Reproductive Medicine. (2005) Fertility preservation and reproduction in cancer patients. *Fertil Steril*; 83:1622-28.

Cao Y-X, Xing Q, Li L, et al. (2009) Comparison of survival and embryonic development in human oocytes Cryopreserved by slow-freezing and vitrification. *Fertil Steril*; 92:1306-11.

Chen C. (1986) Pregnancy after human oocyte cryopreservation. *Lancet*; 1:884-886.

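### Files close when oocytes are used, discarded or reach year ten, so births from a last or late warming need not be recorded

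*Protocol*

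**What the plan says.** Under Establishment and Maintenance of the Outcome Data (the text runs on under Quality of Life Assessment), the Protocol states two things about follow-up:

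- **Contact.** "Study participants will be contacted on an annual basis" to find out whether stored oocytes were used "for the purpose of initiating a pregnancy, along with the outcome of the attempt". The outcome is not further defined as delivery or infant status.
- **Closure.** A file stays active "until all oocytes have been utilized, disposed of in some other way, or ten years following storage, whichever comes first".

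Two sentences in Study Design bear on the same follow-up. Research Design & Methodology says: "Patients with stored oocytes will be contacted annually to determine the outcome of any oocyte warming procedures". The Duration entry reads: "Until the completion of our investigational study and the patient outcome follow-up one year following oocyte harvest".

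The outcomes the study wants are named elsewhere. The Rationale calls it imperative that data on "the health of infants born following its use be prospectively generated". The Conclusion hopes for "information regarding the future use of cryopreserved oocytes, their survival and viability, pregnancy and live birth outcomes". Anticipated Results & Potential Pitfalls says the findings will "document the long term outcomes from the use of these oocytes (pregnancy rates and rate of birth defects").

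**The concern.** The closing rule follows what happens to the oocytes, but the outcomes of interest arise months after the oocytes are used. Because the earliest event governs, the ten-year limit cannot keep open a file that last use has already closed. A woman who warms all her oocytes in one cycle has only a last warming, so any birth she has falls in the gap.

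The loss is also one-sided. A failed warming is known soon, whereas a delivery takes most of a year. Early closure therefore tends to keep failures and drop deliveries and infant findings. With at most 50 women enrolled, births will be few and each unrecorded one counts.

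**Working it through.** The Protocol gives no figure to reproduce here. The check sets the closing events against the timing of the outcomes and then sizes the gap.

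**Inputs from the Protocol**
- Closing events: all oocytes used, disposed of, or ten years (120 months) after storage, whichever is earliest.
- Contact interval: 12 months.
- Enrolment: up to 50 women.

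**Assumptions not in the Protocol**
- Warming to birth: 8 to 9 months (checked also at 34 to 40 weeks).
- Pregnancy known 2 weeks to 2 months after warming.
- Time from a warming to the next annual call is uniform over 12 months.

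**1. Does any closing event wait for delivery?** No. Last use precedes any resulting birth. Disposal of remaining oocytes can happen during a pregnancy. Year ten is a calendar date. No other text shown keeps a file open to delivery.

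**2. Strict reading: the file closes at last use.** Every birth from a last warming comes after closure.

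**3. Lenient reading: the file closes at the first annual call after last use.** For a warming that leads to a birth *g* months later, the share of births still to come at that call is *g*/12.
- *g* = 8: 8/12 = 0.667
- *g* = 9: 9/12 = 0.750

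In weeks, over 52.18 weeks a year: 34/52.18 = 0.652, 38/52.18 = 0.728 and 40/52.18 = 0.767. The two versions agree.

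**4. What is already known at that call?** With pregnancy known after time *p*, the share known is 1 − *p* divided by one year.
- *p* = 2 months: 1 − 2/12 = 0.833
- *p* = 14 days: 1 − 14/365.25 = 0.962

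So about 83% to 96% of pregnancies would be known. The gap is delivery and infant status, not pregnancy.

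**5. The ten-year limit.** A birth falls before month 120 only if the warming falls before month 120 − *g*.
- *g* = 8: month 112, an exposed window of 8/120 = 6.7% of the follow-up period
- *g* = 9: month 111, an exposed window of 9/120 = 7.5%

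These are shares of calendar time, not of warmings or births.

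**6. Who is contacted?** The follow-up section addresses all study participants. Research Design & Methodology addresses women with stored oocytes, a group that a woman leaves when she uses her last one. The two do not match for exactly the women at issue.

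**The case against.** The best reply is that the closing sentence governs file status and does not limit data collection. The same paragraph asks all study participants for the outcome of an attempt, so a sensible investigator would record that outcome before closing the file. The consent form and the call and email scripts, to which the Protocol refers, are not shown and may already carry follow-up to delivery. The percentages belong to one constructed reading: the strict reading exposes all last-warming births and the purposive reading none. The Protocol gives no rate or timing of warming, so the number of births affected is unknown and could be zero. The infant outcomes are stated as hopes or anticipated results. At the 10% pregnancy rate per thaw cycle cited in the Rationale, one cycle in each of 50 women would give about 50 × 0.10 = 5 pregnancies, too few to estimate a birth-defect rate with useful precision under any rule.

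Much of this stands as a limit on size. The intent to capture outcomes is clear, births from earlier warmings can be picked up at later calls, and the number lost cannot be given. It does not remove the problem. The closing rule is explicit, and it can be met before the outcome exists. Clinical outcomes and successful pregnancies appear in the Objective and Hypothesis, so they are more than background. Few expected births make each one more valuable to a descriptive series. If the scripts or consent form do extend follow-up, the Protocol sentence is out of line with them and still needs correcting.

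Two points carry little weight. The parenthesis after the Research Design sentence, which ends at embryo transfer, can be read as listing the procedures and not as limiting the outcome. The Duration entry is ambiguous against the ten-year file, but it does not itself prove the gap.

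**Conclusion.** The concern holds. As written, the closing rule does not secure delivery and infant status for a woman's last warming, for a warming followed by disposal of the remaining oocytes during pregnancy, or for a warming in the last 8 to 9 months before year ten. That conclusion comes from the wording alone.

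For last warmings, the exposed share of births is all of them on the strict reading and about 67% to 75% if closure waits for the next annual call. The latter rests on the assumed 8 to 9 months to birth and evenly spread calls. Confidence is moderate, because the consent form and contact scripts were not available. It should be fixed, and an amendment is enough.

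**What to change.** Make three wording changes:

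1. **Closing rule.** Keep the three closing events and add: *No file closes under any of these conditions until the outcome of every warming begun before that point has been recorded, including delivery and infant status at birth for any ongoing pregnancy, or the woman has withdrawn or is documented as lost to follow-up.*
2. **Research Design & Methodology.** Extend the annual contact to women with a pending warming outcome as well as those with oocytes in storage.
3. **Duration.** State that the one-year point is the quality-of-life assessment and that outcomes of oocyte use are followed under the closing rule.

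Check the consent form and the call and email scripts against the new wording and align them where they differ, since some contacts may fall after year ten.

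Beyond the amendment itself, the cost is one or two extra contacts for the few women who are pregnant when their file would otherwise close. Status at birth will not capture defects recognised later. If those are wanted, the Protocol must name a later assessment, at further cost.
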